## **9.0 Case Report Forms and Source Documents**

All clinical data associated with this registry will be collected and reported electronically (eCRF) via a web address and secure password. Patient questionnaires will be completed

on paper forms and sent to United BioSource Corporation (UBC) Data Management for entry by mail.

At the enrollment visit, the Physician will complete the Enrollment eCRFs by obtaining and recording all available required information, including visit date, demographic data, concomitant diseases and concomitant medications.

At subsequent visits corresponding to the schedule of assessments ([Table 1](#)), the Physician will complete the appropriate eCRF by obtaining and recording all available information. Since this is an observational registry conforming to usual clinical practice, data from patient visits that most closely correspond to the recommended schedule of assessment at Months 1 and 3 (if applicable), 6, 12, 18, 24, 30, 36, 42, 48, 54, 60, 72, 84, 96, 108 and 120 will be accepted. Retrospective SAEs and AESI will be captured during the enrollment visit.

Source documents are defined as original documents, data and records. This may include hospital records, clinical and office charts, laboratory data/information, pharmacy dispensing and other records, recorded data from automated instruments, microfiches, photographic negatives, microfilm or magnetic media, and/or x-rays. Data collected during this registry must be recorded on the appropriate source documents. Patient completed questionnaires (DICHAQ, CHQ-PF50); parent's global assessment of patient's disease activity (VAS), parent's assessment of patient's pain (VAS), physician's global assessment of disease activity (VAS) and joint assessments will be documented on a paper Case Report Form, which will be sent to UBC for data entry.

Paper questionnaires or eCRFs will be generated for patients that have discontinued from the Registry and where consent/assent to data release has been obtained for the HCP data collection on an annual basis. Patients will be followed for hospitalizations, surgeries, death, and any Adverse Event of Special Interest as defined in [Section 7.1.3](#) via a paper questionnaire or eCRF through the first 5 years of the patient's enrollment date. HCPs will document any occurrence of hospitalizations, surgeries, death, malignancies, and/or

CHF annually via a paper questionnaire or eCRF beginning at Year 6 through Year 10. Completed questionnaires will be entered into the database.

The Physician(s)/institution(s) will permit registry-related monitoring, audits, IEC/IRB review, and regulatory inspection(s), providing direct access to source data documents.

## **10.0 Data Analysis Plan**

The primary objective of this registry is to evaluate the long-term safety of Humira. The secondary objective of this registry is to evaluate the long-term effectiveness of Humira. See Section 5.0 for complete objectives.

[figure not shown]
### **10.1 Analyzable Populations**

The All Treated Population is defined as patients who receive at least one dose of MTX or Humira in the registry. The All Treated Population will be used for analysis of safety and effectiveness.

In addition, the Intermittent Treatment Population, defined as Humira patients who have at least one treatment interruption in Humira dosing, will be used in the analysis of safety and effectiveness.

A treatment interruption (TI) for a patient will be defined as a period of > 70 consecutive days during which a patient does not receive any Humira injections. The first day of the TI will begin 71 days after the previous injection of Humira. For patients who receive another Humira injection after the TI, the last day of the TI will be defined as the day before the patient receives the next injection (i.e., the first post-TI Humira injection; see Figure 3). Note that a patient may have multiple TIs. If a patient fails to restart Humira within 1 year of the last Humira injection, then that patient will not be included in the Intermittent Treatment Population.

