**Figure 3. Treatment Period and Treatment Interruption (TI) Period**

## 10.2 Demographics and Registry Enrollment Characteristics

Baseline characteristics: age, sex, race/ethnicity, weight, height, duration of JIA, JIA disease activity and onset type of JIA Disease onset, Rheumatoid factor (RF+, RF-), HLA-B27, body mass index (BMI), prior therapies for JIA, concomitant polyarticular JIA medications, and Humira dosage and exposure duration.

Demographics and baseline characteristics will be summarized for the All Treated Patient Population. Descriptive statistics for demographics, effectiveness, and safety parameters will be presented. Number of patients with non missing values, mean, and standard deviation will be provided for continuous variables. Counts and percentages will be provided for categorical variables. The number and percentage of patients who discontinue from the registry will be summarized, overall and by reason for discontinuation. Duration of observation in the registry, registry exposure duration and total exposure duration will be summarized as follows:

Duration of observation period = the last date of registry participation (inclusive of HCP process) – enrollment date to MTX or Humira in the registry + 1

Registry exposure duration:

(MTX arm) = last MTX dose date in the registry or the first Humira dose date in the registry whichever is earlier – first MTX dose date in the registry + 1 (The first MTX dose in the registry will be on or after the enrollment date).

(Humira arm) = last Humira dose date in the registry – first Humira dose date in the registry + 14 days – total days of any treatment interruptions (The first Humira dose in the registry will be on or after the enrollment date).

Total exposure duration:

(MTX arm) = last MTX dose in the registry or the first Humira dose date in the registry whichever is earlier – first recorded MTX dose (initial dose) + 1.

(Humira arm) = last Humira dose date in the registry – first recorded Humira dose (initial dose) + 14 – total days of any treatment interruptions. For patients who rolled over from Study DE038 and were in the Placebo arm during the double-blind period of this study, the duration of the double-blind period will be subtracted from total exposure.

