### **10.3.4 Analysis of Patients with Treatment Interruption (TI)**

The following summaries will be performed for patients with a treatment interruption (TI) in Humira injections. The SAEs and AEs of Special Interest collected through the HCP process will not be included in these summaries.

For the first group of safety summaries, all patients will be categorized into 2 groups: patients who have at least one TI and patients who have no TI. Two summaries of SAEs

and Adverse Events of Special Interest will compare descriptively patients who have at least one TI and patients who have no TIs:

Crude incidence: The number and percent of patients experiencing SAEs or Adverse Events of Special Interest will be tabulated for each SOC and PT.

Events per 100 patient years of observation: The number of SAEs and Adverse Events of Special Interest per 100 patient years of observation will be tabulated for each SOC and PT.

For the second group of safety summaries the longest TI will be considered and adverse event rates (SAE and Adverse Events of Special Interest) during the last on-drug period prior to the TI (i.e., the pre-TI period) will be compared to adverse event rates during the first on drug period following the TI (i.e., the post-TI period).

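### Because a TI needs no restart, permanent stops of Humira fall in the TI group of the safety comparison, and the one-year rule removes whole patients rather than single gaps

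*Supplement*

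**What the plan says.** Section 10.1 of the protocol sets these rules:

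- A TI is "defined as a period of > 70 consecutive days during which a patient does not receive any Humira injections". It begins 71 days after the previous injection.
- An end date is given only for those who restart: "For patients who receive another Humira injection after the TI, the last day of the TI will be defined as the day before" the next injection. Nothing is said about the end of a gap that never closes.
- The Intermittent Treatment Population is "defined as Humira patients who have at least one treatment interruption in Humira dosing". It carries an exclusion: "If a patient fails to restart Humira within 1 year of the last Humira injection, then that patient will not be included". The section also states: "Note that a patient may have multiple TIs".

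Section 10.3.4 does not build its first safety summaries on that population. There, "all patients will be categorized into 2 groups: patients who have at least one TI and patients who have no TI", and the one-year rule does not reappear. The second set of summaries uses each patient's longest TI. Under Table 2 the pre-TI window closes 70 days after the last injection before that TI, and the post-TI window opens at the first injection after it.

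Section 10.2 computes Humira exposure as last dose date minus first dose date plus 14 days, less "total days of any treatment interruptions".

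Three other places matter. Sections 6.0 and 6.6 provide for continued follow-up of patients who stop Humira. Section 6.8.1 lists failure to restart within 1 year as a reason for treatment discontinuation. Section 7.1.3 counts any event leading to premature discontinuation as an AESI, with a narrower rule for the direct-to-HCP process.

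**The concern.** Section 5.0 makes the effect of interruptions on safety and effectiveness part of the secondary objective. A patient returns from an interruption but not from a permanent stop. If both carry the same label, the TI versus no-TI table becomes in part a comparison of patients who stopped with patients who stayed on drug. A patient who stops because of an adverse event and remains in the registry adds that event to the AESI count and is placed in the TI group because of it. Crude incidence in that group is then raised by definition, whatever an interruption itself does.

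The one-year rule causes a different problem for Section 10.4.2, which asks whether response is regained once Humira is restarted. If a later stop removes the patient altogether, patients whose restart did not last are the ones more likely to be lost, and whether a restart lasts is close to the outcome being studied. It is reasonable to leave out patients who never restarted, since they cannot inform recovery. The fault lies in losing patients who did restart.

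**Working it through.** The protocol gives no TI frequency, so there is no figure to reproduce. The check applies the written rules to four constructed histories, with injections every 14 days from Day 1 and observation to Day 1826 (illustrative choices).

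| Patient | Dosing | TI days | Section 10.3.4 group | Intermittent Treatment Population |
|---|---|---|---|---|
| 1 | Last dose Day 365, no restart | open from Day 436 | TI | out |
| 2 | Gap Day 365 to Day 485 (120 days), then continuous | 436–484 | TI | in |
| 3 | As patient 2 to the restart, then last dose Day 695 | 436–484; open from Day 766 | TI | out |
| 4 | As patient 2, plus a gap Day 891 to Day 1300 (409 days), then continuous | 436–484; 962–1299 | TI | out |

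**Grouping.** Patient 1 never resumed Humira, yet shares the TI group with patient 2, who had a true interruption.

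**One-year rule.** Patients 3 and 4 both had a 120-day gap closed by a restart, the same TI that qualifies patient 2. How they are lost depends on what the last Humira injection means:

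- If it means the last injection before each gap, patient 4 is removed by the 409-day gap. Patient 3 is also removed if the final stop counts as a TI.
- If it means the last injection ever, patient 3 is removed and patient 4 stays.

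As long as the patient is the unit of exclusion, each reading discards a valid earlier TI for at least one of them. Section 10.4.2 points the other way. Where the last assessment falls before Week 12 after the restart, it carries forward the last value before discontinuation, so it expects restarters who then discontinue to be analysed. A patient like patient 3 who stops before Week 12 and is observed off drug for over a year is covered by that rule but excluded from the population.

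**Longest TI.** In patient 3 the first TI lasts 484 − 436 + 1 = 49 days. If the final stop is treated as the longest TI, no injection follows it and Table 2 has no post-TI start. The pre-TI window then runs to Day 695 + 70 = Day 765 and takes in the whole restart period, Days 485 to 695.

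**Exposure.** Subtracting closed gaps only:

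- Patient 1: 365 − 1 + 14 = 378 days.
- Patient 3: 695 − 1 + 14 − 49 = 659 days.
- Patient 4 (last dose Day 1818): 1818 − 1 + 14 − 49 − 338 = 1,444 days, where 338 = 1299 − 962 + 1.

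On one literal reading, the open gap is also subtracted up to the end of observation. Patient 1 then loses 1826 − 436 + 1 = 1,391 days, giving 378 − 1,391 = −1,013. Patient 3 loses 1826 − 766 + 1 = 1,061 days, giving 659 − 1,061 = −402.

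For patient 4 the current text works as it should. If gaps over 1 year ceased to be TIs everywhere, 338 off-drug days would return to exposure (1,444 + 338 = 1,782), and events in that gap would no longer be excluded from the treatment-emergent summaries.

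**The case against.** The protocol separates interruption from permanent discontinuation elsewhere. Section 6.6 treats them in different paragraphs, and Section 6.8.1 turns a gap with no restart in 1 year into a discontinuation. The second set of summaries in Section 10.3.4 presupposes a restart, and Section 10.3 names the Intermittent Treatment Population for the intermittent-treatment summary. This is good evidence of intent. But Section 10.3.4 says all patients and splits on any TI; if the population were meant, patients off drug for over a year would have no defined place in a two-way split.

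The carry-forward rule in Section 10.4.2 suggests that restarters who discontinue are meant to stay. That also stands, but it conflicts with the exclusion wording and does not repair it.

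Two stronger readings are tempting. The first is that the exposure formula yields negative exposure. That requires an end date for an open gap, which the protocol never supplies. The formula runs from first to last dose, and the treatment-emergent window ends 70 days after the last dose, before a final gap begins. The negative values show only why a clarifying sentence is worth adding.

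The second is that the approximately 68% dropout in Section 10.6 means the TI group consists mostly of discontinuers. That figure is registry dropout used to reduce patient-years. Patients who leave within 70 days of their last dose show no TI, and Section 10.3.4 omits events from the HCP process. Even if 68% stood in for stopping Humira, the result would depend on unknowns. Let r be the fraction with a restarted TI (assumed 5% to 30%) and o the fraction of stoppers observed beyond 70 days (assumed 25% to 100%). The share of never-restarters in the TI group is 500 × 0.68 × o × (1 − r) divided by that quantity plus 500 × r. It ranges from 59.5/209.5 = 28% to 323/348 = 93%. The documents do not say where in that range the registry would fall.

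Finally, Figure 3 and the SAP to which the protocol refers were not available and may refine these rules. The point rests on definitions that the protocol itself fixes.

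**Conclusion.** The point holds as a defect of definition. As written, permanent stoppers observed for more than 70 days belong to the TI group in Section 10.3.4. Because events leading to discontinuation are AESI, this pushes crude incidence in that group upward. For events per 100 patient-years, the stoppers' off-drug observation also enters the denominator, so the net direction there is not fixed. The size of the bias cannot be derived from the documents.

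The per-patient exclusion discards valid restarted TIs on every reading that keeps the patient as the unit, and it conflicts with Section 10.4.2. Table 2 has no post-TI period when the final stop is the longest TI.

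The consequences are bounded. These are descriptive summaries serving part of the secondary objective. The observational rates in Section 10.3.1 do not use TI, and the power statement in Section 10.6 is unaffected. The change should be made, but it does not threaten the primary safety summary.

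**What to change.** 1. In Section 10.3.4, classify as TI only a gap over 70 days that is closed by a Humira injection within 1 year of the previous one. Show patients whose only gap is a permanent stop or exceeds 1 year as a separate group, or end their time at last dose plus 70 days. State where a gap still open and shorter than 1 year at last contact belongs.
2. In Section 10.1, apply the one-year rule to each gap, so that earlier qualifying TIs stay in the Intermittent Treatment Population. Choose the longest TI for Table 2 among qualifying closed gaps.
3. In Sections 10.2 to 10.3.3, keep subtracting from exposure, and excluding from the treatment-emergent windows, every gap over 70 days between two injections, including those longer than 1 year. State that the open gap after the last dose is not subtracted.

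The restriction in item 1 must not be carried into item 3, or off-drug time would count as exposure. The cost is definition wording, programming and one more column in the TI tables. Section 6.6.11 already collects dosing dates and interruptions through Year 10.

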**Figure 3. Treatment Period and Treatment Interruption (TI) Period**

## 10.2 Demographics and Registry Enrollment Characteristics

Baseline characteristics: age, sex, race/ethnicity, weight, height, duration of JIA, JIA disease activity and onset type of JIA Disease onset, Rheumatoid factor (RF+, RF-), HLA-B27, body mass index (BMI), prior therapies for JIA, concomitant polyarticular JIA medications, and Humira dosage and exposure duration.

Demographics and baseline characteristics will be summarized for the All Treated Patient Population. Descriptive statistics for demographics, effectiveness, and safety parameters will be presented. Number of patients with non missing values, mean, and standard deviation will be provided for continuous variables. Counts and percentages will be provided for categorical variables. The number and percentage of patients who discontinue from the registry will be summarized, overall and by reason for discontinuation. Duration of observation in the registry, registry exposure duration and total exposure duration will be summarized as follows:

Duration of observation period = the last date of registry participation (inclusive of HCP process) – enrollment date to MTX or Humira in the registry + 1

Registry exposure duration:

(MTX arm) = last MTX dose date in the registry or the first Humira dose date in the registry whichever is earlier – first MTX dose date in the registry + 1 (The first MTX dose in the registry will be on or after the enrollment date).

(Humira arm) = last Humira dose date in the registry – first Humira dose date in the registry + 14 days – total days of any treatment interruptions (The first Humira dose in the registry will be on or after the enrollment date).

Total exposure duration:

(MTX arm) = last MTX dose in the registry or the first Humira dose date in the registry whichever is earlier – first recorded MTX dose (initial dose) + 1.

(Humira arm) = last Humira dose date in the registry – first recorded Humira dose (initial dose) + 14 – total days of any treatment interruptions. For patients who rolled over from Study DE038 and were in the Placebo arm during the double-blind period of this study, the duration of the double-blind period will be subtracted from total exposure.

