## 6.0 Investigational Plan

Patients, who agree to participate in the registry, will be followed for up to 10 years (within a registry arm), including patients who discontinue Humira (monotherapy or combination therapy with MTX) or MTX (without Humira). For patients who switch from the MTX arm to the Humira arm, the 10-year follow-up period will start at the time of enrollment into the Humira arm. This registry will assess the incidence and rate of Humira (monotherapy or combination therapy with MTX) or MTX observational and treatment-emergent SAEs, Adverse Events of Special Interest (AESI) and Pregnancy in patients diagnosed with moderately to severely active polyarticular or polyarticular-course JIA through Year 5. AESI are listed in Section 7.1.4 of this protocol. Starting at Year 6, patients will be followed annually for SAEs, a subset of AESI that includes congestive heart failure (CHF), malignancies, AEs at least possibly related to and/or leading to discontinuation of registry treatment, and pregnancies through Year 10. For polyarticular JIA patients 2 to < 4 years of age in countries with available local approval for this group

of patients at the time of consent to the registry, SAEs, all AESI, and pregnancy (at the age when a patient can become pregnant) will be collected for the full 10 years.

Patients who have discontinued or will discontinue from the registry (prior to completion of 10 years) will be contacted to determine interest in enrollment into the direct to HCP (Health Care Provider) follow-up process as described in Section 6.2. AESI, hospitalizations, surgeries and death as listed in Section 7.1.3 and Section 7.1.4 will be collected through Year 5 for those patients who choose to participate in the direct to HCP follow-up process. Starting at Year 6, patients will be followed annually for congestive heart failure, malignancies, hospitalizations, surgeries, and death through Year 10. Any other AEs, SAEs, and/or pregnancies should be reported according to normal spontaneous reporting procedures, and they are not subject to the requirements of this protocol. In countries with available local approval at the time of consent, polyarticular JIA patients 2 to < 4 years of age who discontinue for any reason, will be offered the opportunity to participate in the direct to HCP follow-up process and will be followed for AESI, hospitalizations, surgeries, and death annually for the full 10 years.

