The procedures outlined in [Table 1](#) are discussed in detail in this section, the exception of the collection of AE information, which is discussed in [Section 7.1.1](#) and Informed consent/patient authorization which is discussed in [Section 8.0](#). For patients participating in the HCP follow-up process, follow-up is done annually as defined in the protocol and only AESI, surgeries, hospitalizations, and death are collected through completion of Year 5. Starting from Year 6 from initial registry enrollment, patients participating in the HCP questionnaire process will be followed annually for congestive heart failure, malignancies, hospitalizations, surgeries, and death through Year 10 ([Figure 1](#)). For polyarticular JIA patients 2 to < 4 years of age in countries with available local approval for this group of patients at the time of consent to the registry and participating in the HCP follow-up process will have AESI, hospitalizations, surgeries and deaths collected for the full 10 years as defined by the protocol ([Figure 2](#)). Any other AEs, SAEs, and/or pregnancies should be reported according to normal spontaneous reporting procedures, and they are not subject to the requirements of this protocol.

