#### **6.6.5 Safety Data Collection**

The following safety information will be collected from the time the parental consent and patient assent forms are signed: AEs of Special Interest and SAEs. The Physician will assess and record the AE in detail including the date of onset, description, severity, time course, duration and outcome, relationship of the AE to treatment, an event diagnosis, if known, and any action(s) taken. For SAEs considered "possibly related," "probably not related" and "not related" to the registry treatment, the Physician will provide the alternative etiology of the event. Information about medications taken to treat the SAE or the Adverse Event of Special Interest will be collected.

During the first 5 years of the registry, all available patient data, including SAEs, AESI as defined by the protocol and pregnancies will be collected at each doctor's visit. However, SAEs, AESI and pregnancy information can be collected at any time during the registry, not only at each doctor's visit. During Years 6 through 10 of the registry, patient data will be collected annually, including SAEs, a subset of AESI that includes congestive heart failure, malignancies, AEs at least possibly related to and/or leading to discontinuation of registry treatment, and pregnancies (Figure 1). Polyarticular JIA patients 2 to < 4 years of age, in countries with available local approval for this group of patients at the time of consent to the registry, will have SAEs, AESI, and pregnancy (potentially at the age when patient can become pregnant) collected for the full 10 years as defined by the protocol (Figure 2). Patients who develop an SAE or Adverse Events of Special Interest (AESI) while in the registry will be followed throughout the patient's participation in the registry until satisfactory conclusion or until 70 days following the last registry dose (whichever is longer).

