### 7.1.3 Adverse Events of Special Interest

The Physician will monitor each patient for clinical and laboratory evidence for pre-defined Adverse Events of Special Interest at the Baseline visit and on a routine basis through Year 10 of the registry as mentioned in Section 6.5 Registry Duration.

AEs of Special Interest for this registry include:

Serious and nonserious opportunistic infections including the following bacterial, fungal, viral, and parasitic infections: Aspergillus, Blastomyces, Candida, Coccidioides, Cryptococcus, Cytomegalovirus, Histoplasma, Listeria, Nocardia, Paracoccidioides, Pneumocystis, Toxoplasma, Tuberculosis, Herpes, Bacillary angiomatosis, Mucormycosis, Progressive Vaccinia, Zygomycosis, BK virus, and JC virus.

Hypersensitivity reaction to Humira injection

Lymphoma

Hepatosplenic T-cell lymphoma

Non-melanoma skin cancer (NMSC)

Leukemia

Other malignancies (except lymphoma and NMSC)

Immune reactions including lupus, lupus-like reactions, and severe allergic reactions

CNS demyelinating disorders (including MS and Guillain-Barré syndrome and optic neuritis)

Hematologic events that are serious or lead to permanent discontinuation of treatment (e.g., aplastic anemia, granulocytopenia, granulocytes maturation Arrest, Leucopenia, Neutropenia, Pancytopenia, and Thrombocytopenia)

Hepatic events that are serious or lead to permanent discontinuation of treatment (e.g., persistent liver function test abnormalities, acute liver failure, and other serious hepatic events)

Vasculitis

Diverticulitis

Intestinal perforation

Congestive heart failure (CHF)

Severe CPK elevations (defined as CTC grade 3 and above) and associated clinical syndromes

New onset seizure disorders defined as any new epilepsy disorder diagnosed within the timeframe of the registry

Antiphospholipid syndrome and associated autoantibodies

New onset or worsening of Psoriasis

All events leading to premature discontinuation of treatment (Note: limited to only Adverse Events of Special Interest [listed above] leading to premature discontinuation for patients participating in the direct to HCP process)

All events that are probably or possibly related to treatment (Note: limited to only Adverse Events of Special Interest [listed above] that are probably or possibly related to treatment for patients participating in the direct to HCP process)

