### **10.3.1 Analysis of Observational SAEs and AEs of Special Interest**

The number and percent of patients experiencing SAEs and AEs of Special Interest during the registry, regardless of whether the AEs are reported during or after the Humira or MTX treatment, will be tabulated by body system and Medical Dictionary for Drug Regulatory Activities (MedDRA®) preferred term. Rates (event per 100 patient year of observation) of SAEs and AEs of Special Interest and the 95% confidence interval will be provided. The AEs summaries will also include SAEs and AEs of Special Interest collected through the HCP process. The last contact date is defined as the last date of registry or direct to HCP process participation, whichever occurs later.

The summaries will be provided using data from the first day in registry through the last contact irrespective of drug treatment duration.

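### Observational SAE and AESI rates keep counting person-time after some event classes stop being collected, so the rates for those classes are biased low

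*Supplement*

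**What the plan says.** **Denominator.** Protocol Section 10.2 defines observation time from "Duration of observation period = the last date of registry participation (inclusive of HCP process", minus the enrollment date, plus one day. Section 10.3.1 uses it for every event type: "Rates (event per 100 patient year of observation) of SAEs and AEs of Special Interest and the 95% confidence interval will be provided". The same section fixes the end of follow-up ("The last contact date is defined as the last date of registry or direct to HCP process participation, whichever occurs later") and puts HCP events in the numerator ("The AEs summaries will also include SAEs and AEs of Special Interest collected through the HCP process"). Nothing cuts person-time at Year 5, at the move to HCP follow-up, or by event class.

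**Collection.**
- Registry, ages 4 to 17. Section 6.0: "Starting at Year 6, patients will be followed annually for SAEs, a subset of AESI that includes congestive heart failure (CHF), malignancies". The subset also includes AEs at least possibly related to treatment or leading to its discontinuation. Section 6.6.5 agrees: "patient data will be collected annually, including SAEs, a subset of AESI that includes congestive heart failure, malignancies".
- HCP follow-up. The text after Table 1 in Section 6.6 says that "only AESI, surgeries, hospitalizations, and death are collected through completion of Year 5". From Year 6 it lists only CHF, malignancies, hospitalizations, surgeries and death. Sections 6.0 and 6.6 send any other AE or SAE to spontaneous reporting, outside the protocol.
- Patients aged 2 to < 4 at consent keep full AESI collection for 10 years in both settings.
- Section 7.1.3 limits the related and treatment-ending categories to listed AESI for HCP patients. It also says that AESI are monitored "on a routine basis through Year 10 of the registry as mentioned in Section 6.5 Registry Duration", with no restriction after Year 5. The current Section 6.5 gives no AESI schedule.

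**Neighbouring analyses.** Sections 10.3.2 and 10.3.3 divide by exposure time and exclude HCP events. Section 10.3.4 also excludes HCP events but reports rates per 100 patient-years of observation.

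**The concern.** A rate is interpretable only if its person-time is time in which the event would have been recorded. Person-years in which an event class is not collected add to the denominator and nothing to the numerator, so the rate and its confidence interval move toward zero.

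Long-term safety of Humira is the primary objective, with MTX as the reference group, and the error runs in the favourable direction. Its size depends on how follow-up divides between Years 1 to 5, Years 6 to 10 and HCP time. If the arms differ in that mix, their rates will differ for reasons unrelated to drug.

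**Working it through.** **Step 1. Collection by setting (ages 4 to 17), from Sections 6.0, 6.6, 6.6.5 and 7.1.3.**

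| Event class | Registry Y1–5 | Registry Y6–10 | HCP Y1–5 | HCP Y6–10 |
|---|---|---|---|---|
| CHF, malignancies | yes | yes | yes | yes |
| SAEs involving hospitalization, surgery or death | yes | yes | yes | yes |
| Other SAEs | yes | yes | only if a listed AESI | only if CHF or malignancy |
| Other listed AESI: non-serious, unrelated, not treatment-ending | yes | **no** | yes | **no***|
| Related or treatment-ending AEs outside the AESI list | yes | yes | **no*** | **no*** |

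*Unless recorded as a hospitalization, surgery or death.

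The denominator runs across all four columns for every row. Two components are therefore diluted: (a) listed AESI other than CHF and malignancies after Year 5, limited in the registry to non-serious, unrelated, non-treatment-ending cases; and (b) in HCP time, SAEs that the questionnaire does not ask about, together with unlisted related or treatment-ending AEs.

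**Step 2. Reproduce the plan's figures (Section 10.6: 500 Humira patients, 5 years, 68% dropout, about 1,500 patient-years, about 97% power).** With exponential dropout the hazard is −ln(0.32)/5 = 0.2279 per year. Person-years in Years 1 to 5 are 500 × 0.68/0.2279 = 1,492, which matches the stated 1,500. At 1,500 patient-years, 2.8 against 4.8 per 100 gives 42 against 72 expected events. The exact two-sided Poisson test at 0.05 has 97.8% power, in line with the stated figure.

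**Step 3. Registry part of the dilution.** Assume a constant event rate, and let q be the share of the class still captured in Years 6 to 10. Then

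reported/true = (PY₁₋₅ + q × PY₆₋₁₀) / (PY₁₋₅ + PY₆₋₁₀).

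If the same hazard continues, PY₆₋₁₀ = 500 × (0.32 − 0.32²)/0.2279 = 477. If everyone left at Year 5 completes Year 10, it is 500 × 0.32 × 5 = 800.

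| Pattern | PY Y1–5 | PY Y6–10 | q = 0 | q = 0.5 |
|---|---|---|---|---|
| Same hazard continues | 1,492 | 477 | 0.76 | 0.88 |
| No exit after Year 5 | 1,492 | 800 | 0.65 | 0.83 |
| No dropout at all | 2,500 | 2,500 | 0.50 | 0.75 |

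The understatement is 24% to 50% for a component not collected after Year 5, and 12% to 25% if half its cases are still captured. For registry SAEs, q = 1 and the ratio is 1.00.

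**Step 4. HCP part.** With h the HCP share of observation time and q the share of the class that the HCP form captures, reported/true = 1 − h(1 − q). The documents give neither. For h from 10% to 50% (assumed), the ratio runs from 0.90 to 0.50 at q = 0 and from 0.975 to 0.875 at q = 0.75. In Section 10.3.4, HCP events are excluded while HCP time is counted, so q = 0 applies to every event class there.

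**Step 5. Between arms (extreme illustration).** With a true ratio of 1, q = 0, one arm at 0.50 and the other at 0.76, the apparent rate ratio is 0.66 or 1.52.

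**The case against.** The best defence is that little is lost. Registry SAEs are collected through Year 10. So are CHF, malignancies, and related or treatment-ending AEs. Hematologic and hepatic events count as AESI only if serious or leading to permanent discontinuation, so they stay captured in the registry. No AESI category disappears as a whole, because its serious cases remain SAEs. Serious infection, on which the sizing rests, is an SAE. Malignancy and CHF, the reason for the second five years, are collected in both settings. The rates are descriptive, and an SAP, which is not shown, could refine the denominators.

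Most of this stands, and it limits both scope and size. A reader might infer that Years 6 to 10 dilute SAE rates generally, or that AESI rates are simply halved. The documents do not support either reading. The 24% and 50% figures apply to a component with no capture after Year 5, and 50% also requires no dropout.

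A reader might also infer that HCP follow-up never collects SAEs. It always asks about hospitalizations, surgeries and death, and Section 6.7.2 speaks of SAE reporting throughout the HCP process. Sections 6.0 and 6.6 nevertheless place SAEs outside the listed items beyond the protocol, so part of the SAE numerator is not systematically collected there.

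The appeal to an unseen SAP does not remove the point. Sections 10.2 and 10.3.1 state the formula outright and do not defer it.

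**Conclusion.** The concern holds for two components: the AESI no longer collected after Year 5 in patients aged 4 to 17, and, in HCP time, the SAEs and unlisted related or treatment-ending AEs that its questionnaire does not cover. Their observational rates are biased low by the stated rule.

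For the registry part, the understatement is about 24% on the plan's own dropout, up to 50% with no dropout, and 12% to 25% if half the cases are still captured. These figures assume a constant event rate and read the 68% as exponential registry exit. Section 10.6 uses that 68% to size drug exposure, and patients who stop drug are encouraged to stay in the registry, so Years 6 to 10 could carry more weight than the 24% case allows. The HCP effect has a known direction but no supportable size.

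The treatment-emergent rates (Sections 10.3.2 and 10.3.3) share only the registry part of the AESI problem: dosing is recorded through Year 10 and exposure has no Year 5 cut, but HCP time does not enter. Section 10.3.4 has a plain numerator and denominator mismatch. Registry SAE rates in Years 6 to 10, and CHF and malignancy rates, are sound in this respect.

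**What to change.** In Sections 10.2 and 10.3.1 to 10.3.3, count events and person-time only within the collection window of each event class:

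- **Full AESI rates:** Years 1 to 5, or 10 years for patients aged 2 to < 4 at consent. Include HCP time for listed AESI in the observational rates; use registry time only for the related and treatment-ending categories.
- **Registry rates for Years 6 to 10:** report separately for the AESI subset still collected (CHF, malignancies, related or treatment-ending AEs) and for serious AESI, so that late events are kept.
- **All-SAE rates:** registry time only, through Year 10.
- **CHF, malignancy, hospitalization, surgery and death (observational rates):** to last contact including HCP, restricted to time that a questionnaire covers. The current text does not say what period the first questionnaire covers.
- **Section 10.3.4:** remove HCP time from the denominator, since HCP events are excluded.
- **Text:** reconcile Section 7.1.3 with Sections 6.0 and 6.6.5 on AESI collection after Year 5.

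The cost is a derived end-date per event class and some extra tables. No new data are needed. Some rates will become less favourable.
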